9.4 DATA SOURCES

In the UK, nearly all residents are registered in a general medical practice that uses electronic medical records. Some of those records are available for research purposes in the CPRD. CPRD contains diagnostic and prescribing information recorded by general practitioners (GPs) as part of their routine clinical practice in the UK. The database currently contains data for over 13.2 million patients with research-quality data from 680 UK practices; 5.69 million of these patients are active (still registered with a contributing GP practice) [[R14-5257](#)]. Patients registered are representative of the whole UK population in terms of age and sex.

Data collection happens as part of normal clinical care of patients in participating practices on a daily basis. Patients are included in the primary care dataset from their first until their last contact with the participating practice. Data are collected by practices and usually uploaded to the CPRD secure servers on a monthly basis.

Protocol for non-interventional studies based on existing data**BI Study Number 0205-0537****c25002535-01**

Proprietary confidential information © 2018 Boehringer Ingelheim International GmbH or one or more of its affiliated companies

The CPRD contains data on demographic information, prescription details, clinical events (symptoms, diagnoses), preventive care provided, tests, immunisations, specialist referrals, hospital admissions and their major outcomes, and details relating to death. It should be noted that the CPRD only has prescription data but not the actual dispensing data. Data are largely recorded by general practice staff using version 2 Read codes, a hierarchical clinical classification system containing over 96, 000 codes. Numerical data on additional clinical measures (e.g. height, weight, blood pressure, alcohol intake) can also be recorded during consultations. Prescriptions issued by the GP are automatically recorded with a product name and British National Formulary code, alongside the dosage instructions and quantity. Results of laboratory tests ordered by the GP are commonly added to the patient record via electronic links to laboratories. Data fed back to the GP from other sources may also be entered into the patient record by practice staff; this might include information from secondary care such as key diagnoses, discharge data from hospitals, or follow-up information from specialist clinics. [[R16-1231](#)]

In addition, the following CPRD-linked data will be used in this study:

- Hospital Episode Statistics (HES) Admitted Patient Care (HES APC) data
- HES Accident and Emergency (HES A&E) data
- Patient Level Index of Multiple Deprivation

HES APC data are collected on all admissions to National Health Service (NHS) hospitals in England. HES APC also covers admissions to independent sector providers (private or charitable hospitals) paid for by the NHS. HES APC does not cover accident and emergency (A&E, emergency department) attendances or outpatient bookings. In the financial year 2014/15 (April to March), 18,731,987 hospital episodes from 451 different NHS hospital trusts (known as ‘providers’) were recorded in HES APC. HES APC provides detailed clinical, demographic and organizational information for each Finished Consultant Episode. Data on drugs prescribed through hospital pharmacies to inpatients are not available in HES APC [[R18-0523](#)]. In this study, HES APC will be used to assess hospitalization (all-cause, respiratory disease related, or asthma or lower respiratory condition related) in the year prior to the index date among patients who were treated at English NHS health care providers. HES A&E data consist of individual records of patient care administered in the accident and emergency setting in England. These data are a subset of national A&E data collected by NHS England to monitor the national standard that 95% of patients attending A&E should wait no longer than 4 hours from arrival to admission, transfer or discharge. A&E data are submitted by A&E providers of all types in England. Data collected includes details about patients’ attendance, outcomes of attendance, waiting times, referral source, A&E diagnosis, A&E treatment (drugs prescribed not recorded), A&E investigations and Health Resource Group [[R18-0524](#)]. In this study, HES A&E will be used to ascertain A&E attendance for asthma or low respiratory conditions, which will be used to calculate the number of asthma exacerbation in the year prior to the index date.

Patient Level Index of Multiple Deprivation (IMD) data are small area level measures of relative deprivation that are available for linkage to CPRD GOLD data through the patient and/or practice postcode. These measures can be used as a proxy to socio-demographic and socio-economic data which are generally poorly recorded in the primary care data as they do not directly relate to a patient's care. Data is provided as quintiles or deciles of the deprivation

Protocol for non-interventional studies based on existing data**BI Study Number 0205-0537****c25002535-01**

 Proprietary confidential information © 2018 Boehringer Ingelheim International GmbH or one or more of its affiliated companies

score or rank to prevent disclosure of patient or practice area. The postcode of the practice or patient residence is mapped to lower layer Super Output Area (LSOA) using a postcode lookup file [[R18-0524](#)]. In this study, Patient Level Index of Multiple Deprivation data will be used to ascertain patient level IMD.

9.5 STUDY SIZE

The study size is dependent on the uptake of Spiriva Respimat for asthma in the CPRD. [Table 1](#) provides a range of estimates for different prevalence estimates of disease (or characteristics). The numerator represents the number of patients with the comorbidity of interest and the denominator represents the number of new users in the population. With 500 patients we would have adequate confidence intervals around these estimates.

Table 1 Precision of estimates for proportion measures

Number of New Users	95% Confidence Intervals for Various Prevalences of Diseases (%)				
	1%	2%	5%	7%	10%
500	0.4-2.3	1.1-3.6	3.4-7.3	5.1-9.6	7.7-12.9
800	0.5-2.0	1.2-3.2	3.7-6.7	5.4-9.0	8.1-12.3
2,000	0.6-1.5	1.5-2.7	4.1-6.0	6.0-8.2	8.8-11.3
5,000	0.8-1.3	1.6-2.4	4.4-5.6	6.3-7.7	9.2-10.9

A feasibility check was conducted to assess the number of patients in the tiotropium group, after application of the study inclusion and exclusion criteria. The result indicated that between September 2014 and December 2017, the number of patients in the tiotropium group was 935.

9.6 DATA MANAGEMENT

This study will use the in-house CPRD data set. Data management, tabulations, and graphics will be carried out with SAS 9.4 (SAS Institute, Cary NC). Source code of data management and data analyses will be kept for inspection at least for five years after publication of the results.

9.7 DATA ANALYSIS

All the analyses will be conducted with SAS 9.4 (SAS Institute, Cary NC).

9.7.1 Main analysis

The primary objective of this study is to describe the clinical and socio-demographic characteristics of asthma patients prior to the initiation of Spiriva Respimat for the treatment of Asthma. For this objective, patient baseline characteristics (as described in the “outcomes” and “covariates” section) will be tabulated and summarized for all new users of Spiriva Respimat. Means, standard deviations, medians, minimum, maximum, and interquartile range

(IQR) will be used to present continuous variables, counts and percentages will be used to present categorical variables.

The secondary objective of this study is to describe and compare the characteristics of asthma patients who initiated Spiriva Respimat to asthma patients who initiated a higher dose of ICS/LABA FDC, or LTRA, or alternatively those who switched from the previous ICS/LABA FDC to a new ICS/LABA FDC. For this objective, patient characteristics (as described in the “outcomes” and “covariates” section) will be tabulated for the patients that initiated or switched to the other available treatments separately, using measures as described for the patient baseline characteristics of Spiriva.

Patient characteristics (as described in the “outcomes” and “covariates” section) will be compared among patients who initiated Spiriva Respimat and patients in other treatment groups. Analyses will be conducted in unmatched cohorts and differences between spiriva restinmat and each of the other exposure groups will be assessed using absolute standardized differences (ASD), where an ASD of at least 10% will be considered a meaningful difference [[R16-1227](#)].

9.7.3 Missing values

No imputation will be done for missing values. For all covariates, missing values will be presented as a separate category.

9.8 QUALITY CONTROL

This protocol will be strictly followed in the study. All changes to this protocol will be documented in protocol amendments.

The study protocol has been written following the Code of Conduct by the European Network of Centres for Pharmacoepidemiology and Pharmacovigilance (ENCePP) [[R15-4870](#)] that provides a set of rules and principles for post-authorisation studies with regard to the best practices and transparency, thereby promoting scientific independence of such studies. The study will be registered to the ENCePP’s E-register and the results will also be published on the same site.

Protocol for non-interventional studies based on existing data**BI Study Number 0205-0537****c25002535-01**

Proprietary confidential information © 2018 Boehringer Ingelheim International GmbH or one or more of its affiliated companies

The study protocol also follows the key elements of the Guideline for Good Pharmacoepidemiology Practices (GPP) by International Society for Pharmacoepidemiology [[R11-4318](#)], and the recent draft Guidance for Industry and FDA Staff “Best Practices for Conducting and Reporting Pharmacoepidemiologic Safety Studies Using Electronic Healthcare Data Sets” [[R15-4859](#)].

The statistical analytic approach will be reviewed/repeated by a second analyst to ensure quality control.

The study report will be reviewed, approved and archived per BI SOP and conducted upon ISAC approval.

9.9 LIMITATIONS OF THE RESEARCH METHODS

The main analysis will exclude patients with other respiratory disease (e.g., COPD). This will exclude asthma-COPD overlap patients and some other patients and the results may not be representative to all asthma patients. However, Spiriva has both asthma and COPD indications. Therefore, for asthma-COPD overlap patients, the reason for initiating Spiriva Respimat can be unclear in existing data. Since the primary objective is to describe the characteristics of asthma patients prior to the initiation of Spiriva Respimat for the treatment of Asthma, it would be reasonable to exclude asthma-COPD overlap patients,

This study is based on existing data. It is possible that misclassification may happen for the measurement of comorbidities. However, we will use all the available data before the index date to minimize the possibility of misclassification.

Some covariates such as smoking status, alcohol use, BMI, pulmonary function, and eosinophil count may not be well recorded in CPRD. In the analyses we will present missing data as a separate category.

Some information may be recorded very infrequently or not at all in CPRD, e.g., number of people in a household, over-the-counter medication use, prescriptions in secondary care. These variables will not be assessed in this study.

The CPRD only includes patient data captured from general practitioners. Although some information about patient contacts with secondary care could be manually entered into the patient record, details about these specialty visits and hospital admissions (including dates, diagnoses, tests performed, length of stay) may be incomplete.

The CPRD may not be representative of all practices in the UK based on geography and size. There are certain patient groups that are missing from primary care records, such as prisoners, private patients, some residential homes and the homeless. Thus, selection bias cannot be ruled out. However, studies suggested that CPRD patients are broadly representative of the UK population in terms of age and sex. Patients are also comparable to the UK census in

terms of ethnicity, and comparable to the Health Survey for England for body mass index distribution in most patient subgroups.

The HES APC data and HES A&E data only have data for patients from England.

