8. RESEARCH QUESTION AND OBJECTIVES

The primary objective of the study is to describe the clinical and socio-demographic characteristics of asthma patients at the time of the initial prescription of Spiriva Respimat for the treatment of Asthma within a general clinical population using the GOLD database within Clinical Practice Research Datalink (CPRD).

A secondary objective will be to describe and compare the characteristics of asthma patients who initiated Spiriva Respimat to asthma patients who initiated a higher dose of ICS/LABA FDC, or LTRA, or alternatively those who switched to a new ICS/LABA FDC.

Protocol for non-interventional studies based on existing data

BI Study Number 0205-0537

[figure not shown]
c25002535-01

 Proprietary confidential information © 2018 Boehringer Ingelheim International GmbH or one or more of its affiliated companies

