9.2 SETTING

The study population will be asthmatic patients who were prescribed ICS/LABA FDC before the index date and who initiated Spiriva Respimat, or received a higher dose of ICS/LABA FDC, or initiated LTRA, or switched to a new ICS/LABA FDC from the previous ICS/LABA FDC in the UK during the study period (September, 2014-December 31, 2017). Selection of the above therapies is based on the BTS/SIGN guideline (see [figure 1](#) in [section 7](#)). These therapies are all options at adult asthma treatment steps 3 or 4. Although theophylline and

Protocol for non-interventional studies based on existing data**BI Study Number 0205-0537****c25002535-01**

Proprietary confidential information © 2018 Boehringer Ingelheim International GmbH or one or more of its affiliated companies

beta-agonist tablet are also options for add-on therapy at steps 3 and 4, we will not include these two in the current study because they are not widely used in the U.K.

The index prescription will be one of the follows:

- The first prescription of Spiriva Respimat during the study period;
- The first prescription of ICS/LABA FDC with a higher daily dose (any higher dose) (compared to the last prescription) during the study period (if there are more than 1 dose increase during the study period, only the first dose increase will be used in the analyses);
- The first prescription of LTRA during the study period;
- The first prescription of a new ICS/LABA FDC during the study period.

The index date is defined as the date of the index prescription.

In this study, all patients will be required to have at least 1 year of continuous up-to-standard (UTS) registration in the CPRD prior to index date to determine indications of use and previous treatments.

The in- and exclusion criteria of this study are as follows:

Inclusion criteria:

- Aged 18 years and above at the index date
- At least 12 months of continuous registration prior to the index date in a practice contributing up to standard (UTS) data to the CPRD
- Had a diagnosis of asthma before the index date (In this study, an asthma diagnosis is defined as at least one medcode for asthma prior to the index date. Please refer to [annex 3](#) for the detailed medcodes for asthma and the related Read terms)
- Being treated with ICS/LABA FDC before the index date (at least one prescription within 3 months before the index date)

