9.3 VARIABLES

All the variables will be identified based on data recorded on the index date (date of dispensing/initiation of the exposure), or when a characteristic was not recorded on the index date, during the pre-index period (the one closest to the index date), unless otherwise specified.

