9.3.2 Outcomes

9.3.2.1 Primary outcomes

The primary outcome is whether patient has Cardiac arrhythmias on the index date or in the year prior to the index date. Cardiac arrhythmias is defined as having the following readcode in the above mentioned time period:

medcode	readcode	readterm
17597	327..00	ECG: supraventricular arrhythmia
19707	328..00	ECG: ventricular arrhythmia
29371	328Z.00	ECG: ventricular arrhythmia NOS
97780	G559.00	Arrhythmogenic right ventricular cardiomyopathy
6503	G57..11	Cardiac arrhythmias
426	G577.00	Sinus arrhythmia
31690	G57yA00	Re-entry ventricular arrhythmia
53893	Gyu5a00	[X]Other specified cardiac arrhythmias
26670	2432.00	O/E - pulse irregularly irreg.
18746	662S.00	Atrial fibrillation monitoring
45773	6A9..00	Atrial fibrillation annual review

Protocol for non-interventional studies based on existing data

BI Study Number 0205-0537

c25002535-01

Proprietary confidential information © 2018 Boehringer Ingelheim International GmbH or one or more of its affiliated companies

9479	7936A00	Implant intravenous pacemaker for atrial fibrillation
92361	793M000	Perc translum ablat pulmon vein to lft atrium conduct system
105554	8CMW200	Atrial fibrillation care pathway
57832	9Os..00	Atrial fibrillation monitoring administration
90187	9Os0.00	Atrial fibrillation monitoring first letter
90188	9Os1.00	Atrial fibrillation monitoring second letter
90189	9Os2.00	Atrial fibrillation monitoring third letter
90190	9Os3.00	Atrial fibrillation monitoring verbal invite
90191	9Os4.00	Atrial fibrillation monitoring telephone invite
63350	9hF..00	Exception reporting: atrial fibrillation quality indicators
39114	9hF1.00	Excepted from atrial fibrillation qual indic: Inform dissent
2212	G573.00	Atrial fibrillation and flutter
1664	G573000	Atrial fibrillation
35127	G573300	Non-rheumatic atrial fibrillation
96277	G573400	Permanent atrial fibrillation
96076	G573500	Persistent atrial fibrillation
23437	G573z00	Atrial fibrillation and flutter NOS

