- Allergic rhinitis
- Sinusitis
- Charlson comorbidity index [[R08-1584](#)]
- Cataract
- Osteoporosis
- Obesity

Concomitant prescriptions

- Asthma-related prescriptions in the year prior to index date
 - Short-acting beta agonists
 - Inhaled long-acting beta agonists (on top of ICS/LABA FDC)
 - Inhaled corticosteroid (ICS) (on top of ICS/LABA FDC)
 - Oral corticosteroid
 - Theophylline
 - Leukotriene Receptor Antagonist (LTRA)
 - Azithromycin,
 - Mucolytics
- Cardiovascular medications
 - Cardiac Glycosides
 - Thiazides
 - Loop diuretics
 - Antiarrhythmics
 - Beta blocker
 - Vasodilator Antihypertensive Drug
 - Centrally Acting Antihypertensive Drugs
 - Alpha-adrenoceptor Blocking Drugs
 - Drugs affecting the renin-angiotensin system

- Angiotensin Converting Enzyme Inhibitors
- Angiotensin II receptor blockers
- Renin Inhibitors
- Other antihypertensives
- Nitrates
- Calcium channel blockers
- Oral anticoagulants
- Heparin and other low molecular weight heparins
- Aspirin
- Antiplatelet
- Lipid-regulating Drugs
 - Bile Acid Sequestrants (lipid-regulating Drugs) - including Colesevelam
 - Ezetimibe (only in combination with Statin)
 - Fibrates
 - Statins
 - Nicotinic Acid Group
 - Omega-3 Fatty Acid Compounds
 - Other lipid-regulating drugs
- Glucose-lowering agents
- Non-steroidal anti-inflammatory drugs
- Psycholeptics
- Antipsychotics
- Antidepressants
- Agents for dementia

For concomitant medications used for diseases other than asthma the look-back time period will be limited to 180 days prior to the index date to increase the likelihood that the medications were used concomitantly. Concomitant medications will be categorized as current use (up to and including 60 days before index date) and past use (use any time prior to the 60 days before index date).

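### The unlimited look-back for comorbidities mixes old, resolved pneumonia, delirium and acute sinusitis with recent episodes, so the 10% ASD rule on those rows can mask or create a difference at initiation

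*Protocol*

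**What the plan says.** Section 9.3.3 lists pneumonia, delirium and sinusitis among the comorbidities and gives none of them a window of its own. The general rule in section 9.3 takes the index date or, failing that, a record "during the pre-index period (the one closest to the index date), unless otherwise specified". It sets no limit on how far back that period runs. Section 9.9 then settles the matter for comorbidities: "It is possible that misclassification may happen for the measurement of comorbidities. However, we will use all the available data before the index date", with less misclassification as the stated aim. The registration criterion in section 9.2, "At least 12 months of continuous registration prior to the index date", is a minimum and not a cap.

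Other variables do have a recent window. For the primary outcome, "The primary outcome is whether patient has Cardiac arrhythmias on the index date or in the year prior to the index date". Section 9.3.2.2 gives the secondary outcome the same window, and section 9.3.3 uses one year for exacerbations, hospitalizations and asthma prescriptions. For non-asthma medication, "the look-back time period will be limited to 180 days prior to the index date".

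Section 8 places the description "at the time of the initial prescription of Spiriva Respimat for the treatment of Asthma". Section 9.7.1 compares Spiriva Respimat with each other group by ASD, "where an ASD of at least 10% will be considered a meaningful difference".

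**The concern.** A longer look-back helps for a chronic disease: once diagnosed it is still present, and more history means fewer missed cases. For an illness that has resolved, more history adds patients who are flagged but did not have the condition around the index date. For these rows the reason given in section 9.9 therefore works against the time point set in section 8.

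The study is meant to detect channeling (sections 7 and 9.1), and section 7 says the results may guide the choice of propensity-score variables in later studies. A reader of the pneumonia row could not tell whether a flagged difference reflects recent illness or distant history, or whether an unflagged row hides a recent difference. This holds even if record length is the same in all groups.

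**Working it through.** **Inputs from the protocol.** Open look-back for comorbidities (9.9); at least 12 months of record (9.2); ASD threshold of 10% (9.7.1). The protocol gives no ASD and no prevalence for these conditions, so it has no figure of its own to reproduce on this point.

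**Assumed inputs, for illustration only.** Yearly rates of 1% to 3%, record lengths of 1 to 20 years, and old history of 10% to 15%.

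**Formulas.**

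- ASD = |p1 − p2| / √{[p1(1 − p1) + p2(1 − p2)] / 2}
- Any-time prevalence over T years = 1 − (1 − earlier yearly rate)^(T−1) × (1 − last-year rate)

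**Case A: a recent difference with equal earlier history.** The last-year rate is 3% (Spiriva) vs 1% (comparator), and the earlier yearly rate is 1% in both.

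- One-year row: 0.02 / √[(0.03 × 0.97 + 0.01 × 0.99) / 2] = 0.02 / 0.1396 = 14.3%. Flagged.
- Fifteen years: comparator 1 − 0.99^15 = 13.99%; Spiriva 1 − 0.99^14 × 0.97 = 15.73%. ASD = 0.01737 / 0.3556 = 4.9%. Not flagged.
- In the comparator at 15 years, (13.99 − 1) / 13.99 = 93% of flagged patients had no episode in the last year.

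**Case B: as A, with earlier yearly rates 1.25 times higher in the Spiriva group (1.25% vs 1%).** At 15 years, Spiriva is 1 − 0.9875^14 × 0.97 = 18.66% against 13.99%. ASD = 0.04668 / 0.3689 = 12.7%. Flagged.

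| Years of record | ASD, case A | ASD, case B |
|---|---|---|
| 5 | 8.2% | 11.8% |
| 10 | 6.0% | 12.0% |
| 15 | 4.9% | 12.7% |
| 20 | 4.2% | 13.3% |

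**Case C: no recent difference, unequal old history.** Last-year prevalence is 3% in both groups, and old history is 15% vs 10%. Any-time prevalence is 1 − 0.97 × 0.85 = 17.55% vs 1 − 0.97 × 0.90 = 12.70%. ASD = 0.0485 / 0.3575 = 13.6%. The any-time row is flagged although recent status is identical.

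**Case D: a stable difference in a rare condition.** Yearly rates are 2% vs 1% throughout. The one-year ASD is 8.2%, not flagged. Over five years, 1 − 0.98^5 = 9.61% vs 1 − 0.99^5 = 4.90%, and ASD = 0.04707 / 0.2583 = 18.2%, flagged. Here the short window is the one that misses.

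Cases A and C show the any-time row masking and creating a difference. Case B shows how small an imbalance in older history undoes the masking. Case D shows that a one-year row alone would not be a clean replacement.

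**The case against.** A reader might infer that old episodes always swamp recent ones and push real differences below 10%. The documents do not support that. Case A rests on identical rates in every year but the last. The protocol gives no rates, and section 7 says the UK indication requires a severe exacerbation in the previous year on top of ICS/LABA with a stated minimum ICS dose. A Spiriva group whose older history also differs is therefore at least as plausible, and cases B and D then go the other way. This part of the objection stands in full.

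Other points carry some weight:

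- An ever-history flag is a legitimate descriptive choice, and the study tests no hypothesis.
- The protocol does not follow a rule of short windows for acute and long windows for chronic conditions. Its one-year outcomes include codes for permanent atrial fibrillation and chronic congestive heart failure. The contrast with the outcomes shows that a one-year window is available, not that a principle has been broken.
- Sinusitis is listed without a code list and may include chronic disease. The point applies to its acute form.
- Recent illness is partly captured by the one-year exacerbation, hospitalization and asthma-prescription variables. That cover is incomplete: it does not isolate these three diagnoses, and section 9.9 notes that the hospital and A&E linkage covers England only.
- Condition-level windows are often left to an analysis plan. Here, however, section 9.9 itself states one rule and its justification for all comorbidities, and that justification does not fit these rows.

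**Conclusion.** The point holds in a limited form. For pneumonia, delirium and acute sinusitis, the open look-back gives a row that does not describe status at initiation, and applying the 10% rule to it can mask or create a difference. The direction depends on whether older history is balanced between groups. In the illustrations, a one-year ASD of 14.3% becomes 4.9% or 12.7% on 15 years of record, and an ASD of 13.6% appears with no recent difference at all. These figures rest on assumed rates and show the mechanism only; they do not predict the study's results.

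The consequence is minor. Three rows of a long covariate list are affected, and neither the primary nor the secondary outcome is.

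**What to change.** In sections 9.3.3 and 9.9, report two rows for each of pneumonia, delirium and sinusitis: one for a record on the index date or in the year before it (the window already used for the outcomes), and one for any time before the index date. Compute the ASD for both. Base statements about status at initiation on the one-year row and statements about history on the any-time row. Restrict the misclassification argument in section 9.9 to chronic comorbidities, and leave those on full history.

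The cost is one date condition on data already held and three extra table rows. Counts in the one-year rows will be low, so a rare condition may not reach 10% there even when a stable difference exists (case D). That is why the any-time row should stay beside it.

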9.3.1 Exposures

The study drug of interest is Spiriva Respimat. The exposure in the Spiriva group will be initiation of Spiriva Respimat. The exposure in the comparator group will include: 1) initiation of LTRA; 2) an increase in daily dose of ICS/LABA FDC; and 3) switching to a new ICS/LABA FDC.

To make sure that patients who initiated Spiriva Respimat or LTRA are new users of these drugs, patients who initiated Spiriva Respimat must have no exposure to tiotropium before the index date, and patients who initiated LTRA must have no exposure to LTRA before the index date.

An increase in daily dose of ICS/LABA FDC refers to any increase in the daily dose. If there was more than 1 dose increase during the study period, only the first dose increase will be included in the analysis.

Switching to a new ICS/LABA FDC refers to patients who switched to a new ICS/LABA FDC with different drug ingredient that was not prescribed during the pre-index period. If there was more than 1 switch during the study period, only the first switch will be used in the analysis.

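### Comorbidities are taken from records of unequal length and compared by unadjusted ASD, so a between-group difference in record length, if there is one, can create or hide a flagged difference

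*Protocol*

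**What the plan says.** The comorbidities listed in Protocol section 9.3.3 (pneumonia, depression, myocardial infarction, stroke, sinusitis, osteoporosis, the Charlson index and others) carry no time window of their own. The default in section 9.3 is a value on the index date or, failing that, "during the pre-index period (the one closest to the index date), unless otherwise specified"; the length of that period is not defined. Section 9.9 settles it for comorbidities: "we will use all the available data before the index date to minimize the possibility of misclassification".

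The only bound on record length is the inclusion criterion in section 9.2: "At least 12 months of continuous registration prior to the index date in a practice contributing up to standard (UTS) data to the CPRD". There is no maximum. Section 9.4 adds that "Patients are included in the primary care dataset from their first until their last contact with the participating practice", so the window differs from patient to patient.

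For the secondary objective, section 9.7.1 states: "Analyses will be conducted in unmatched cohorts". Spiriva Respimat is contrasted with each other group by ASD, "where an ASD of at least 10% will be considered a meaningful difference". Length of registration before the index date is not among the 9.3.3 characteristics, and no adjustment for it is described.

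Other variables do have fixed windows: one year for the two cardiac outcomes, exacerbations, hospitalisations and asthma prescriptions, and 180 days for non-asthma medication.

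**The concern.** The chance that a condition has ever been recorded rises with the number of years in which it could have been. With an open-ended look-back, two groups with the same underlying morbidity show different prevalences if one has been registered longer. An unadjusted ASD cannot separate that from a real difference between patients. The reader cannot separate it either, because record length is not reported.

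Section 9.9 presents the full look-back only as protection against misclassification. It does not say that under-recording may then differ between groups. The secondary comparison is meant to show channeling of prescribing, and section 7 says the results can also inform the choice of propensity-score variables in future studies. An artefact in these rows could therefore be carried forward.

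**Working it through.** **The plan's own figures.** The only calculated figures in the protocol are the confidence intervals in Table 1 (section 9.5). The Wilson interval reproduces 19 of the 20 cells; the other differs by 0.1 in one limit. The table concerns precision within one group and does not bear on this point.

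**Inputs from the protocol.** All pre-index data for comorbidities (9.9); minimum record 12 months, no maximum (9.2); unmatched ASD with a 10% cut-off (9.7.1); index dates from September 2014 to December 2017, a span of about 3.3 years (9.2).

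**Assumptions, not in the protocol.** A constant yearly rate r of first recording, equal in both groups, tried at 0.5% to 3%; group record lengths T of 5 to 12 years. No record lengths are given, so these are ranges and not estimates.

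**Formulas.** Share ever recorded: p = 1 − exp(−r × T). ASD = 100 × |p1 − p2| / √{[p1(1 − p1) + p2(1 − p2)] / 2}.

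**Worked case.** With r = 2% per year and T = 5 vs 7, p1 = 1 − exp(−0.10) = 0.0952 and p2 = 1 − exp(−0.14) = 0.1306. The difference is 0.0355, the denominator 0.3160, and the ASD 11.2%.

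**Same true rate, unequal record length:**

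| Rate per year | Years of record | Share recorded | ASD | Reaches 10%? |
|---|---|---|---|---|
| 2% | 5 vs 7 | 9.5% vs 13.1% | 11.2% | yes |
| 2% | 8 vs 10 | 14.8% vs 18.1% | 9.0% | no |
| 2% | 8 vs 11 | 14.8% vs 19.7% | 13.2% | yes |
| 1% | 5 vs 8 | 4.9% vs 7.7% | 11.6% | yes |
| 1% | 8 vs 11 | 7.7% vs 10.4% | 9.5% | no |
| 1% | 8 vs 12 | 7.7% vs 11.3% | 12.4% | yes |
| 0.5% | 8 vs 12 | 3.9% vs 5.8% | 8.8% | no |
| any | equal | equal | 0 | no |

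**Masking.** Suppose one group has a rate of 1% per year and 8 years of record, and the other 2% per year and 5 years. The shares are 7.7% and 9.5% and the ASD is 6.5%. With 8 years in both groups the shares are 7.7% and 14.8% and the ASD is 22.6%. A true doubling would go unflagged.

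**Index date alone.** The 3.3-year span is the largest gap between two patients, not between group means. If one group's index dates were spread evenly over the period and the other's all fell at its end, the means would differ by about 3.3 / 2 = 1.65 years. On an 8-year record that gives ASDs of 3.9%, 5.4%, 7.5% and 9.0% at 0.5%, 1%, 2% and 3% per year. On a 5-year record it is below 10% at 0.5% to 2% and reaches 11.4% at 3%.

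**What a short common window does to a real difference.** For true rates of 1% vs 2% per year, the ASD is 22.6% at 8 years (7.7% vs 14.8%) but 8.1% at 1 year (1.0% vs 2.0%).

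**The case against.** The strongest reply is that the imbalance is supposed, not shown. The protocol gives no record length by group, so neither the size nor the direction of any effect is known. That stands.

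A reader might infer that one group will be flagged as sicker by construction, and might point to the rule that "patients who initiated LTRA must have no exposure to LTRA before the index date", which screens out long records more often than short ones. The protocol does not support that inference. Section 9.3.1 puts the same kind of rule on the Spiriva group (no earlier tiotropium) and requires switchers to move to an ingredient not prescribed in the pre-index period; section 9.2 excludes earlier use of another LAMA in every group. These rules act on both sides of the LTRA and switch contrasts, and the net effect is unknown. A shift in index dates is also a weak route, as the calculation shows.

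The constant-rate model is a simplification. Chronic conditions that are re-coded regularly would be less affected.

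Finally, full look-back is a reasoned choice against missed diagnoses, and a statistical analysis plan could hold a sensitivity table. Both are fair. But the protocol itself fixes the open look-back together with the unadjusted ASD and its cut-off, and its limitations section names only the benefit.

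**Conclusion.** The point holds in conditional form. The protocol combines an open-ended comorbidity look-back, a 12-month minimum record and an unadjusted ASD read at 10%, and does not report record length. If group means differ by some 2 to 4 years, the ASD of a condition with the same true rate in both groups lands around the cut-off: above it in some cases (11% for 5 vs 7 years at 2% per year; 12% for 5 vs 8 years at 1%) and just below it in others (9% for 8 vs 10 years at 2%; 9% for 8 vs 12 years at 0.5%). It would be wrong to say that any gap of that size is enough. With equal record lengths there is no effect. All these figures rest on assumed rates and record lengths.

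The scope is limited to the comorbidity rows of the secondary comparison, and the Charlson index if it uses the same look-back. This does not undermine the study's main aim; it is a gap in the comparison that data already held can close cheaply.

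**What to change.** 1. In sections 9.3.3 and 9.7.1, add years of up-to-standard registration before the index date as a tabulated characteristic, with its ASD for each contrast.
2. Keep the all-data look-back as the main comorbidity table. For the secondary comparison, repeat the comorbidity rows and the Charlson index under one common fixed look-back as a sensitivity analysis, to be read beside the main table where registration length differs. One year is available for every patient; a longer window would have to be restricted to patients with that much registration.
3. Do not make an ASD of at least 10% in both tables a condition for calling a difference meaningful. A short window shrinks true differences, and such a rule would discard real ones.
4. State in section 9.9 that unequal look-back can make misclassification differ between groups.

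The cost is one extra row, one extra table and one sentence, with no new data. Prevalences and ASDs in the fixed-window table will be smaller because older diagnoses are missed, and a longer common window would drop some of the roughly 935 tiotropium patients from that table.
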